Women have persistent risk of acquiring HIV in pregnancy and postpartum and often do not perceive themselves to be at risk (1). In a meta-analysis of 19 studies including 22,803 person-years, HIV incidence in pregnant/postpartum women was 3.8 per 100 p-years, 4.7/100 p-years in pregnancy and 2.9/100 p-years postpartum (Figure 1) (2). These HIV incidence estimates are particularly high given that incidence estimation was among all women (not limited to those with seropositive partners) and appreciable HIV infection occurred despite decreased sexual activity

[figure not shown]

Figure 1: HIV Incidence in pregnancy (2)

Pregnancy and the postpartum period are characterized by dramatic hormonal and immunologic changes, changes in genital mucosa, and epithelial disruption during delivery

with decreased mucosal integrity postpartum (3-6). At the same time, sexual practices change markedly in this period. Sexual activity declines late in pregnancy and early postpartum, and male partners may seek other partners, and bring HIV back to the relationship (7-9). HIV acquisition in pregnancy/postpartum most often occurs among women who are unaware of their partner's HIV status. In Zimbabwe, among 1230 pregnant women, 239 (19%) reported their partner had been HIV tested, of whom 213 knew partner results, and 8 reported a HIV positive partner (0.6% of overall cohort). Only 1 of 14 incident HIV infections in this cohort occurred in a woman in a known serodiscordant partnership (10). Similarly, in a Kenyan cohort of 1310 pregnant women, only 1% reported knowing their partner was HIV positive, and these women had *lower* risk of HIV infection than women with unknown or reportedly HIV negative partners (11). HIV risk may be lower among the select few women who report knowing their partner's HIV-seropositive status because these partners are already on ART or use condoms. Many women do not know their partner's HIV status or believe their partner is HIV negative (12).

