Counseling at universal sites, will use a standardized counseling script to state that PrEP is available for women at risk for HIV, explain that HIV prevalence in the region is high, and will note that women with HIV positive partners or who don't know their partner's status may be at risk. Counseling will specify that women may have their own reasons to feel at risk or to want PrEP. Following standardized counseling, women will select PrEP at the same visit or will be allowed to deliberate on the decision and come back at the next visit with a decision. Women will be informed that it is advisable to use PrEP if they know their partner is HIV positive or if they do not know their partner's status and will be encouraged to bring untested partners to clinic if status is unknown. Women who select PrEP will be welcome to involve their partners in counseling regarding PrEP and those with recently diagnosed HIV positive male partners (via the clinic referral system) will be linked to care following the facilities standard linkage to care procedures.

Table 5: Risk Score Card for HIV acquisition in pregnancy

Risk factor	Value per factor	Score
No. of lifetime sexual partner		
1 point per sexual partner	Enter at least 1	
Male partner HIV status		
Male partner HIV status known or no male partner	0	
Male partner HIV status unknown	6	
Syphilis		
nonreactive	0	
reactive	5	
Total risk score		

Targeted PrEP Clinics, Enrollment Visit (N=10):

Following informed consent and enrollment data collection, the targeted PrEP clinics will provide two inter-related innovations: risk assessment-informed PrEP counselling and partner HIV Self-Test counselling.

Risk Assessment and PrEP Counselling:

The results of the PrEP risk assessment will be used to guide PrEP counselling and the offer of proceeding to the PrEP card-based eligibility assessment. Participants who score greater than 6 on the risk assessment will receive additional PrEP counselling that includes information about specific risk factors tailored to the participant (Table 5). These participants will then elect whether to proceed to the PrEP card eligibility assessment. Women

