who score 6 or less will not be individually counseled about PrEP. However, if they ask for PrEP they will enter the clinical assessment pathway and can be prescribed PrEP if found to be clinically eligible. We anticipate that participants with known HIV-positive partners will self-select for the PrEP eligibility assessment. Women who request PrEP despite not meeting the targeted PrEP criteria will be identified and approached for in-depth interviews to better understand their choices in Component 2 of the study.

Partner HIV Self-Testing:

Women will be offered HIV self-test kits to take to their partner for HIV testing. This will be used to provide further information on partner HIV-status: either initiate women in previously unidentified serodiscordant couples on PrEP at subsequent study visits, or to discontinue PrEP

for women who are able to confirm their partner's HIV-negative status. All women will be offered two self-tests so that they can take the test at the same time as their partner, if they chose to do so. If a woman does not receive the self-test counseling during the first study visit, they will receive self-testing counseling during their next study visit.

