Trained program staff will counsel study participants in the use of self-testing kits including. First, they will assess whether the women believe violence could occur when providing the self-testing kit to their partner. If a woman declines the self-testing kit or fears violence, they will not receive the testing kit and this information will be included in the targeted PrEP administration algorithm.. Women who are comfortable providing a self-test to their sexual partner(s) will be instructed by study staff on the use of an oral fluid based rapid HIV test (OraQuick Rapid HIV-1/2 antibody test, OraSure Technologies, Bethlehem, PA, USA). Study staff will demonstrate how to use the oral self-testing including opening the package, collection of fluid samples, waiting 20-minutes before reading the test, and reading test results. Women will be counseled that it is entirely their choice as to whether to offer a self-test to their partner. Participants will be provided with a one-page summary document that describes the self-testing methods and provided information on receiving confirmation testing and linkages to care in the event their partner(s) test positive. Women will be asked to return to the clinic at their next antenatal care visit to report on the results of their partner's self-test.

DBS collection for confirmatory HIV testing

DBS will be collected using a finger stick from all participants at enrollment and stored for future confirmatory HIV testing should a client seroconvert while in the study. Blood from the finger stick will be placed onto five circles on labeled DBS card and allowed to dry between 2-hours and overnight before storing in a low gas permeability plastic bag with a humidity indicator and stored in a freezer between -20 and -80 degrees at CDC KEMRI laboratory for future assessment.

Targeted PrEP Clinic, Visit 2 (next scheduled antenatal care visit):

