During the second study visit, participants will report the results of their partner's self-test. Partners who are identified as HIV-positive through the self-testing will be referred for HIV confirmatory testing and treatment at the nearest CCC, ideally located in the same facility if possible. Women who report that their partners refused the self-test, did not share the results of their self-test, or were unable to take the test will receive additional PrEP counseling during the second study visit, using the same standardized script as high-risk women identified in the first study visit. Women who do not return for the scheduled study visits or to obtain test results will be contacted by study staff.

PrEP Initiation, Universal and Targeted Arms

Women who elect to start PrEP will receive point of care hepatitis B (HBsAg) and creatinine (Cr) testing. Women who are HBsAg positive or who have estimated creatinine clearance (CrCl) ≤ 50 ml/min will be medically ineligible to initiate PrEP per NASCOP guidelines below.

PrEP Medications

PrEP medication and dosing will follow the 2016 Guidelines on Use of Antiretroviral Drugs for Treating and Preventing HIV Infections in Kenya using the preferred oral TDF/FTC (300mg/200mg) once per day (66).

Follow Up Visits, Universal and Targeted Arms

All participants:

Women will follow the MCH schedule for their routine ANC and postpartum/immunization clinic visits. Study visits will be performed at all subsequent ANC visits and the 6-week, 14-week, 6-month, and 9-month postpartum visits, the visit schedule is outlined in table 4. All women will receive HIV rapid test at follow up visits. The study visits are designed to meet MOH guidelines for PrEP users to receive HIV testing and adherence counselling every three months. Data on risk assessment, partnership characteristics, sexual activity and contraception use, and sociobehavioral factors may be collected at all study visits. Additional data will be collected on infant growth, birth weight and estimated gestation at birth or diagnosed preterm birth (for women who deliver at facilities) and serial growth will be abstracted from MCH cards; z-scores will be calculated using WHO Anthro-Plus. Data on birth outcomes (stillbirth, miscarriage, mortality, congenital anomalies) and birth length will be abstracted from MCH card or interview. We may also collect a small amount of hair from participants and their babies (50 strands).

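### In targeted clinics, a woman who reports a known HIV-positive partner but scores 6 or less has no stated PrEP counselling at enrolment; the protocol relies on her asking

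*Protocol*

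**What the plan says.** Targeted clinics (Protocol, Component 1, e) Study Procedures, Risk Assessment and PrEP Counselling): a score above 6 leads to individual, risk-tailored PrEP counselling and the choice to go on to the PrEP card eligibility assessment. Women "who score 6 or less will not be individually counseled about PrEP", but any who ask enter the clinical pathway and can be prescribed PrEP. On this group the text says only: "We anticipate that participants with known HIV-positive partners will self-select for the PrEP eligibility assessment".

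Score card (Table 5): the row "Male partner HIV status known or no male partner" carries 0 points. Unknown status carries 6, reactive syphilis 5, and each lifetime partner 1, with a minimum of 1.

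Universal clinics (same section, enrolment visit): "Women will be informed that it is advisable to use PrEP if they know their partner is HIV positive".

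Self-testing in the targeted arm: one stated purpose is to "either initiate women in previously unidentified serodiscordant couples on PrEP at subsequent study visits". If a woman declines the kit or fears violence, "this information will be included in the targeted PrEP administration algorithm". At visit 2, women whose partner refused the test, could not take it or kept the result private are counselled "using the same standardized script as high-risk women identified in the first study visit".

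**The concern.** The score treats a known positive partner exactly like a known negative one. The arm meant to match PrEP more closely to risk therefore has no stated prompt for a woman who has just reported a direct exposure, while the universal script addresses her situation by name. The targeted arm also hands out self-tests partly to discover positive partners of low-scoring women, yet a woman who already knows of one has no trigger at enrolment.

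What is at stake is individual protection. The literature review (Pre-Exposure Prophylaxis (PrEP) and Women) regards PrEP as needed in newly diagnosed discordant couples until the partner's treatment has taken effect. The score cannot separate those couples from couples in which the partner is already suppressed; counselling and the eligibility assessment can. Partner HIV status is collected from every participant at enrolment, so a trigger needs no new data.

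The appropriate-use outcome may inherit the same blind spot if it is coded from the Table 5 score.

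**Working it through.** The plan gives no figure on this point, so there is none to reproduce. The check has four steps.

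**1. Score of a woman with a known HIV-positive partner** (inputs: Table 5; cutoff above 6)

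Score = 0 (partner status) + n (lifetime partners, n ≥ 1) + 0 or 5 (syphilis).

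| Syphilis | Score | Not counselled | Counselled |
|---|---|---|---|
| Nonreactive | n | n = 1 to 6 | n ≥ 7 |
| Reactive | n + 5 | n = 1 (score 6) | n ≥ 2 (score ≥ 7) |

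For comparison, unknown partner status gives at least 6 + 1 = 7, so those women are always counselled.

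**2. Search for an override in the enrolment and follow-up procedures**

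| Step | Does it reach her? |
|---|---|
| Enrolment counselling | Not by partner status; by score only |
| PrEP on request | Yes, if she asks |
| Declined kit or feared violence | Goes into an algorithm; no resulting action is stated |
| Visit 2 counselling | Only if the partner refused, could not test or did not share the result, and not at enrolment |
| Positive self-test | The visit 2 text specifies referral of the partner; no PrEP step for the woman is given there, although starting PrEP is a stated purpose of the testing |
| PrEP decision row, Table 6 | Marked at visits after enrolment; does not say that an offer is made |

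No enrolment trigger for a known positive partner appears in the readable text.

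**3. Size of the group** (Literature Review, HIV Acquisition in Pregnancy and Postpartum)

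In the Kenyan cohort "only 1% reported knowing their partner was HIV positive". In the other cohort, of 1,230 women, the figure is 0.6%. Both are assumed to carry over to this trial.

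- Targeted arm: 2,000 × 0.006 = 12; 2,000 × 0.01 = 20.
- Per clinic of 200: 1.2 to 2.

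Share scoring 6 or less: let s be the share of all women above the cutoff and u the share with unknown status, all of whom exceed it. Then P(above 6 | status not unknown) = (s − u)/(1 − u), which is at most s.

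- With s = 0.16 (the Kenyan risk-tool data), at least 0.84 of women whose partner status is not unknown score 6 or less. If women with positive partners resemble that group, 0.84 × 20 = 16.8 and 0.84 × 12 = 10.1.
- With s = 0.20 (the anticipated PrEP share in the targeted arm, read as the share above the cutoff): 0.80 × 20 = 16.0 and 0.80 × 12 = 9.6.
- If they exceed 6 twice as often as the 16% ceiling: 0.68 × 20 = 13.6 and 0.68 × 12 = 8.2.
- They stop being a majority only if half or more exceed 6.

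The 16% cannot describe the cohort behind the 0.6%: there 213 of 1,230 women knew the partner's result, so u = 1 − 213/1,230 = 0.83. The 0.6% is used only for how many women know of a positive partner.

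**4. Outcome coding**

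SAP section 2 defines appropriate use by an unspecified risk cutoff, and the SAP shell table of endpoints ties it to the risk score. If that is the Table 5 score, this woman's PrEP use is coded not appropriate and her non-use appropriate, in both arms. Recoding 12 to 20 women in 2,000 would move an arm's proportion by at most 12/2,000 = 0.6 to 20/2,000 = 1.0 percentage points under the same assumption.

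**The case against.** The case on the other side is substantial. The protocol names exactly this group and says what it expects of them, so nothing was overlooked. A score-guided offer is the strategy under test, and different scripts in the two arms are the randomised contrast, not an inconsistency. There is also an empirical reason: in the Kenyan cohort, women who knew their partner was positive had lower HIV risk than the others, which the protocol attributes to partner treatment or condoms. The passage on newly diagnosed couples covers only part of the group, and the documents do not allow that part to be sized. The targeted-clinic consent form, the algorithm, the figures and the national guidelines the study follows might each prompt a PrEP discussion, and none could be read here. The outcome point is conditional too, since the protocol's aims speak of risk factors and not of the score.

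Most of this stands and keeps the point minor. It does not remove it. An expectation that women will ask is not a procedure, and the sentence on women scoring 6 or less is explicit. Lower average risk argues for weighing the partner's treatment at the eligibility assessment, not for omitting the conversation. Visit 2 already includes counselling that does not depend on the score, so a further trigger of that kind would not undo the strategy.

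A reader might infer that these women are refused PrEP. The documents do not support that: any woman who asks is assessed and can be prescribed it.

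**Conclusion.** A minor safety and consistency gap, worth considering, held with medium confidence. On the readable text, a woman in a targeted clinic who reports a known HIV-positive partner and scores 6 or less receives no individual PrEP counselling at enrolment unless she raises it.

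The group is about 12 to 20 of 2,000 targeted-arm women if the cited 0.6% to 1% applies, most of them probably at or below the cutoff. It would be tempting to take 20 women, or 1 percentage point, as an upper limit or as a number harmed. Neither reading holds: both figures scale with a prevalence borrowed from other cohorts, and the number who would not ask is unknown and could be zero. It would also go too far to infer a biased HIV incidence comparison. The gap is part of the strategy being compared, the group is small, and nothing in the documents shows an effect on incidence. The outcome-coding part holds only if the risk cutoff is the Table 5 score.

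**What to change.** In Risk Assessment and PrEP Counselling, replace the sentence on self-selection with a rule such as: *A woman who reports a known HIV-positive partner receives the same PrEP counselling and the same offer of the PrEP card eligibility assessment as a woman scoring above 6, whatever her score; the partner's ART use and viral suppression are considered in that assessment.* Leave Table 5 and the cutoff unchanged. If the PrEP administration algorithm already contains this rule, bring the section into line with it.

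State in SAP section 2 what the risk cutoff is. If it is the Table 5 score, count a known HIV-positive partner as meeting the criterion in both arms, except where sustained partner viral suppression is reported. Without the exception, a woman who reasonably stays off PrEP because her partner is suppressed would be coded as not appropriate, against the protocol's own rule for stopping PrEP. Make the same change in Protocol Table 7. In the Component 2 interview sampling, do not class a woman who asks for PrEP because of a known positive partner as a low-risk acceptor.

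The cost is one protocol rule, a script change in 10 clinics affecting about 1 to 2 women per clinic under the assumed prevalence, and small edits to the outcome and interview definitions. The downside is a slight departure from a purely score-guided offer.

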## 1. STUDY SUMMARY AND AIMS

**Study Purpose:** The broad objective of this study is to determine the best approach to PrEP delivery in pregnancy using existing MCH systems as a platform for efficiently delivering PrEP to pregnant women.

**Study Design:** This is a cluster randomized clinical trial with 20 ANC clinics in Western Kenya (Siaya and Homa Bay) counties comparing Universal and Targeted PrEP administration. The facility-level cluster randomization will be conducted using a restricted randomization approach based on new antenatal care clinic (ANC) volume, and County. County will be used as a proxy for County differences in HIV prevalence in the restricted randomization approach. In the Universal PrEP arm, PrEP is offered to all and women select whether they want to take it. In the Targeted PrEP arm PrEP is offered to women identified as high risk through a standardized risk assessment and partner self-testing.

**Study Population and Sites:** Twenty ANC clinics in Western Kenya (Siaya and Homa Bay) counties will be randomized, 10 Universal and 10 Targeted PrEP administration. At each clinic women attending antenatal care will be enrolled in the study. Eligibility for enrollment will include age  $\geq 15$  years, pregnancy with the gestational age up to 36 weeks by last menstrual period (LMP) or best available estimate, and tuberculosis negative, plans to reside in area for at least one year postpartum, plans to receive postnatal and infant care at the study facility, and are not currently enrolled in any other studies.

**Study Size:** At least 200 women per clinic (2,000 per ARM)

**Study Duration:** At each clinic, enrollment will occur over an approximately 10-month period (~20 HIV negative women enrolled per month) with a ~1-year period of follow-up to 9 months postpartum (time of routine measles immunizations).

**Treatment Regimen:** PrEP medication and dosing will follow the 2016 Guidelines on Use of Antiretroviral Drugs for Treating and Preventing HIV Infections in Kenya using the preferred oral TDF/FTC (300mg/200mg) once per day

### Primary Aims:

**AIM 1a:** To compare Universal PrEP to Targeted PrEP for outcomes reflecting the balance of PrEP effectiveness and safety:

1. HIV incidence at 9 months postpartum
2. Proportion of women who accepted PrEP

**Sub-Aim 1a.** To compare infant outcomes (growth, birth outcomes, HIV status) between PrEP users and nonusers in combined trial arms.

**AIM 1b:** To compare trial arms for:

1. Proportion of women 'appropriately' on PrEP (based on risk factors)
2. PrEP adherence (DBS) and duration
3. Partners with known HIV status, on ART

**AIM 2:** Health economic evaluation of targeted vs. universal PrEP

**AIM 3:** Assessment of barriers and facilitators of PrEP delivery strategies at the individual patient, healthcare facility, and organizational level

*This analysis plan will focus on Aim 1 except for sub-aim 1a which is in a separate SAP for birth/infant outcomes.*

## **2. STUDY ENDPOINTS**

### **Primary Outcome:**

HIV infection - a new positive HIV ELISA test after a documented negative HIV test (HIV tests will be the tests recommended and used by Kenya MOH during the course of the study)

Appropriately on PrEP –

- a. Initiated (swallowed) PrEP and meeting the risk criterion cutoff
- b. Did not initiate PrEP and low risk

### **Secondary Outcomes:**

PrEP Uptake - ever accepted a PrEP prescription from the MCH clinic

PrEP adherence by DBS - any tenofovir-DP detected, tenofovir-DP detected above specific levels (to be defined; analyses are ongoing to better characterize optimal levels in women in general and pregnant women specifically)

Partner HIV status known by end of follow up- by maternal-report when available. Because partners in both trial arms can access HIV testing at the clinic, this data will be captured from maternal MCH cards as available

Infant outcomes – preterm birth, birthweight, 9-month growth (weight, height)

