For pregnant women, a risk scoring tool has also been developed to help identify those at greater HIV risk (20). This tool, developed and validated using data from 1,304 women living in Kenya, includes the following variables: Partner HIV status unknown, number of lifetime sexual partners, and history of syphilis. Women with a score >6 made up 16% of the population but accounted for 56% of HIV acquisition events.

For pregnant women, risk assessment alone may not identify all women at risk of HIV acquisition during pregnancy. Partner self-testing is a strategy that has been successfully used to identify previously unknown HIV-positive partners of pregnant women in Western Kenya. A recent study demonstrated high uptake of partner-testing when multiple self-tests are given distributed to women in antenatal care clinics along with instructions about how to use the tests and counseling about using discretion when determining whether to offer a self-test to sexual partners (21). Of women enrolled in the study, 91% (of 58 participants) reported distributing the self-test to their primary sexual partner *and* being present when their partner used the test (21). The strategy was also found safe for women who participated. This study did exclude a small number of women attending clinics who believed violence could occur from distributing the self-tests, who would likely benefit from PrEP given the risk of violence in their relationship. Including a self-testing intervention that increases partner self-testing will allow this study to identify women who may be categorized as low risk in the risk assessment but have a previously unknown HIV positive partner.

Pre-Exposure Prophylaxis (PrEP) and Women

[figure not shown]
As new studies examine topical microbicides and long-acting PrEP formulations for HIV prevention (22-25), oral PrEP remains a leading candidate for pregnancy given substantial evidence of efficacy, safety, and lack of potential for genital tract irritation that could precipitate preterm birth or ascending infection in pregnancy (26). Increasing partner ART use is another highly effective and complementary approach (27). Condoms, though effective, have not been widely adopted by pregnant/postpartum women, who are usually married and find it difficult to negotiate for condom use in the setting of a presumably stable relationship.

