## **5. STATISTICAL ANALYSES AND DESCRIPTION OF MAIN TABLES**

**AIM 1a:** The proportion of all women enrolled in the study who use PrEP (proportion of women exposed to PrEP) will be compared between trial arms using GEE with a binomial link.

**AIM 1b:** The proportion with 'appropriate' use will be compared between arms using GEE with a binomial link. PrEP adherence will be measured among women on PrEP using DBS TFV drug levels. All women receiving PrEP will have 3-monthly DBS samples available. For each trial arm (10 clinic-cluster) a random subset of 220 DBS will be assessed. TFV drug levels will be compared by trial arm using GEE with a Gaussian link. PrEP duration will be computed for each woman based on self-report and pharmacy records and average duration compared between arms using GEE with a Gaussian link. Reported and confirmed partner with HIV status, proportions of partner HIV positive, unknown and HIV negative status, and reported and confirmed partner ART use will be compared between arms using GEE with a binomial link.

Infant outcomes: mean birthweight and serial weight-for-age z-scores (WAZ), height-for-age z-scores (HAZ), and weight-for-height z-scores (WHZ) will be compared between trial arms using GEE with a Gaussian link. A separate analysis will assess birth and infant outcomes by PrEP exposure in the combined arms.

**AIMS 2-4** will be conducted after the primary analysis and will not be reviewed by the EAC.

---

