**Table 1. Distribution of demographic and clinical characteristics of women by randomization arm**

	N (%) or Median (IQR)		
	Overall	Project arm	
		Universal	Targeted
Demographic characteristics			
Age (years)			
Median age			
<25			
25-35			
≥35			
Marital status			
Currently married			
Divorced/separated			
Cohabiting			
Never married			
Widow			
Education (years)			
Regular employment			
People per room			
Risk assessment characteristics			
No. of lifetime sexual partners			
HIV status of sexual partner(s)			
Positive			
Negative			
Unknown			
No male partner			
RPR reactive			
Pregnancy history			
Gestational age at enrollment (weeks)			
Primigravida			
Previous abortion/miscarriages			
Previous premature birth (<37 weeks)			
Psychosocial scales			
Perceived risk of HIV scale score			
HIV treatment adherence self-efficacy score			
CESD-10 score			
HITS score			

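### The endpoint on known partner HIV status mixes knowledge held at enrolment with knowledge gained during the trial, and the planned analysis leaves enrolment status unused

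*SAP*

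**What the plan says.** SAP section 2 (Secondary Outcomes) defines the endpoint as "Partner HIV status known by end of follow up- by maternal-report when available", supplemented from MCH cards. SAP section 5 (Aim 1b) compares "Reported and confirmed partner with HIV status, proportions of partner HIV positive, unknown and HIV negative status" between arms by GEE. Shell Table 2 carries the endpoint as a row with a risk ratio. None of these places limits the endpoint to women whose partner's status was unknown at enrolment, asks for status newly learned, or adjusts for status at enrolment.

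Enrolment status is collected. The protocol's enrolment questionnaire records partner HIV status for all participants, and SAP shell Table 1 tabulates it by arm as positive, negative, unknown or no male partner.

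Neither document gives the expected share unknown at enrolment or a power calculation for this endpoint. SAP section 3 says only that power for partner characteristics will be ample.

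**The concern.** Partner self-testing is one of the two components of the targeted model, and this is the endpoint on which it would most directly show. A woman who already knew her partner's status adds a success to either arm whatever the kits do. The more such women there are, the smaller the visible difference.

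Clinics also differ in how many women already know, and with 10 clinics per arm a chance imbalance passes into the result. SAP section 3 and the protocol's sample-size section name partner disclosure rates as a balancing factor. The randomisation procedure in SAP sections 1 and 5 uses only county and ANC volume.

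At stake is a blurred or understated reading of the self-testing component when the data to sharpen it are already in hand.

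**Working it through.** **The plan's own figure.** The only sample-size calculation is for HIV incidence. It is reproduced by c = 2 + (1.96 + 0.84)² × [p0(1−p0)/m + p1(1−p1)/m + k²(p0² + p1²)] / (p0 − p1)², with two-sided 5% alpha assumed. For 4% versus 2%, m = 200 and k = 0.2, this is 2 + 7.85 × 0.00037/0.0004 = 9.26, so 10 clinics per arm, as stated. It does not carry over to partner status, for which no rate or clinic variation is given.

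**Share unknown at enrolment (u), from the documents.**
- Low end. In Protocol Table 5, "Male partner HIV status unknown" scores 6 and the lifetime-partner line says "Enter at least 1", so every woman with unknown status scores at least 7. The protocol's literature review reports "Women with a score >6 made up 16% of the population but accounted for 56% of HIV acquisition events". If that cohort was scored the same way, at most 16% were unknown.
- High end. The same review describes a cohort in which 213 of 1,230 pregnant women knew the partner's result: 213/1,230 = 17%, so 83% did not.

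**Dilution.** Let p be the share of initially unknown women who know by the end. The share known at the end is 1 − u(1 − p), so the arm difference is u × (p1 − p0).
- u = 0.16, p = 30% versus 70% (assumed): 88.8% versus 95.2%, or 6.4 points (RR 1.07). Among women unknown at enrolment: 40 points.
- u = 0.83, same p: 41.9% versus 75.1%, or 33 points (RR 1.79).

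**Precision at u = 0.16.** Assume a clinic SD of 10 points in baseline knowledge, and 10 clinics of 200 per arm. Baseline variation reaches the endpoint multiplied by (1 − p), which is 7 points in the universal arm and 3 in the targeted arm.
- SE² = [(0.07² + 0.112 × 0.888/200) + (0.03² + 0.048 × 0.952/200)]/10 = 0.00065. SE = 2.6 points, z = 6.4/2.6, about 2.5. A 10-point clinic SD in conversion adds (0.16 × 0.10)² = 0.000256 per clinic, and z becomes 2.4.
- Among women unknown at enrolment (0.16 × 2,000 = 320 per arm), with a 10-point clinic SD in conversion: SE = √(2 × 0.10²/10 + 2 × 0.21/320) = 5.8 points, z = 40/5.8, about 6.9. Letting the number of unknown women vary between clinics lowers this to about 6.

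**Smaller effect, 25% versus 50%, u = 0.16.** As written: 88% versus 92%, SE = √{[(0.075² + 0.12 × 0.88/200) + (0.05² + 0.08 × 0.92/200)]/10} = 3.0 points, z about 1.3. In simulation with a cluster-level test, power is about 0.24 as written and about 0.90 restricted.

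**Other assumptions.** The same design under an ICC model (0.02 / 0.05 / 0.10):

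| Unknown | Conversion | Power as written | Power, unknown at enrolment |
|---|---|---|---|
| 16% | 25% vs 75% | 0.98 / 0.77 / 0.50 | >0.99 throughout |
| 16% | 25% vs 50% | 0.43 / 0.23 / 0.14 | >0.99 / 0.98 / 0.88 |
| 50% | 25% vs 50% | 0.95 / 0.69 / 0.43 | >0.99 / >0.99 / 0.93 |

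At 83% unknown with 30% versus 70%, both analyses have ample power. With 10-point SDs in baseline knowledge and conversion, the as-written SE is √{[(0.07² + 0.083² + 0.581 × 0.419/200) + (0.03² + 0.083² + 0.249 × 0.751/200)]/10} = 4.7 points, so z is about 7.1. Restricted to 1,660 women per arm, SE = √(0.002 + 0.42/1,660) = 4.7 points, so z is about 8.4.

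**The case against.** Four arguments on the other side have force.

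- **The ceiling is not shown.** A reader might infer that the endpoint is near its ceiling and can barely register self-testing. That takes one end of a 16% to 83% range. The 16% applies this trial's card to another cohort. The protocol also says that many women do not know their partner's status. And 30% versus 70% still gives z about 2.5 at the low end. Using the full 10-point baseline SD as the endpoint's SD would give SE = √(2 × 0.10²/10) = 4.5 points and z = 1.4, but that ignores the (1 − p) factor.
- **The risk ratio depends on scale.** SAP section 5 also compares "proportions of partner HIV positive, unknown and HIV negative status". On the unknown proportion the example is 11.2% versus 4.8%, RR 0.43, the same as 70% versus 30%, so u cancels. This answers the complaint about RR size. It does not remove the noise from baseline differences.
- **Kits are offered to all targeted-arm women**, and reported and confirmed status are both analysed. Kits may therefore change confirmation among women who said they already knew. An analysis confined to the unknown subset would lose this, so the all-women comparison should stay.
- **The subset is not beyond question.** Enrolment status is self-reported after unblinded clinic randomisation and feeds the risk score that guides the offer in one arm, so it could be ascertained differently by arm.

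These points limit the size of the concern and shape the remedy. They do not justify leaving enrolment status out.

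**Conclusion.** The point holds as a matter of efficiency and clarity. As defined, the endpoint shows the effect among initially unknown women scaled by an unstated baseline share, with avoidable clinic noise. If about 16% are unknown, a large effect would probably still be seen, but a moderate one (25% versus 50%) would usually be missed as written and usually found with the restriction. If 83% are unknown, little is lost.

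The figures rest on assumed conversion rates, clinic SDs or ICCs, two-sided 5% alpha and no loss to follow-up. A reader might go further and conclude that a working self-test programme would be reported as ineffective. The documents do not support that: the baseline share is not given, status at enrolment will be visible in shell Table 1, and kit uptake and results have their own shell table. Severity is minor, since one secondary endpoint is affected.

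**What to change.** In SAP section 5 and shell Table 2:

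1. Keep the all-women, intent-to-treat comparison, adjusted for each woman's partner status at enrolment.
2. Add a pre-specified comparison, by the same GEE, of status newly learned by end of follow-up among women whose partner's status was unknown at enrolment.
3. Show the share unknown at enrolment by arm beside that result, as a check on differential ascertainment.
4. State how women with no male partner are counted. Protocol Table 5 groups them with known status, and the endpoint definition is silent.

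The cost is wording and one table row, with no new data. The added comparison uses fewer women, and its subset is defined by a self-report made after allocation was known, so it should sit beside the all-women result and not replace it.
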